1. PROTOCOL SYNOPSIS

Title	Clinical Utility of a Non endoscopic Device EsoCheck and Biomarker EsoGuard as Alternative to Endoscopy for Screening for Barrett's Esophagus in At Risk Population (ASBE) A Randomized Controlled, Virtual Patient Trial
Rationale	A randomized controlled virtual patient trial is a means of obtaining clinical utility data for reimbursement. This trial will obtain clinical utility data on EsoGuard® (EG) a biomarker assay (laboratory developed test/LDT), and EsoCheck® (EC), an FDA cleared, non-endoscopic esophageal cell collection device, which when used in combination has been identified by the AGA and ACG as a reasonable, non-endoscopic alternative for screening of Barrett's Esophagus (BE) and esophageal adenocarcinoma (EAC).
Study objectives	
Primary objective To determine the impact of EsoCheck/EsoGuard on health care provider's decision for endoscopy referral
 
Secondary objective To determine the impact of EsoCheck/EsoGuard on health care provider's patient risk assessment for BE

Study design	A Randomized Controlled, Virtual Patient Trial. Eligible participants will sign the IRB approved ASBE participant Informed Consent Form (ICF). The participants complete two rounds of questions concerning the assessed risk for BE and upper endoscopy referral of 6 patient cases (clinical vignettes). Per round, there will be 3 different questionnaires consisting of 6 clinical vignettes (A/B/C). Participants will be randomized to questionnaire A, B or C according to the randomization scheme.
Study population	Primary care physicians and other physicians whose scope of practice includes disease screening, and/or diagnosis and management of patients with esophageal disease. 
 At least 80% of the overall study population will be primary care physicians, family medicine physicians, and other general practitioners; ≤20% will be other types of physicians/specialists.
Number of participants	Minimum of 100. Around 200 will be invited to participate.
Expected duration of accrual	Approximately 3, but up to 6 months.

2. INTRODUCTION AND SCOPE

EsoCheck® (EC) is an FDA cleared, non-endoscopic cell collection device designed to sample cells from a targeted region of the esophagus; EsoGuard® (EG) is a laboratory developed test (LDT) performed in a Clinical Laboratory Improvement Amendment (CLIA) certified and College of American Pathologists (CAP) accredited lab that utilizes set of genetic assays and algorithms which examines the presence of cytosine methylation at 31 different genomic locations on the vimentin (VIM) and Cyclin-A1 (CCNA1) genes. Using EsoCheck and EsoGuard in combination may offer an accurate, lower cost, minimally invasive, non-endoscopic, approach to screen for BE with and without dysplasia, and for esophageal adenocarcinoma (EAC), as compared with the current gold standard, namely diagnostic upper endoscopy of the esophagus plus biopsies.

EsoCheck/EsoGuard has been clinically validated in a developmental study published in 2018 and shown to have a >90% sensitivity and >90% specificity in non-endoscopic detection of BE or EAC (Moinova 2018). EsoCheck administration is a simple, non-endoscopic, office-based procedure that can be performed by a variety of healthcare providers including physicians, nurse practitioners, physician assistants, nurses and others. It allows for planned, point-of-care screening of the at-risk patient population to provide a convenient and early datum for providers to assist in medical decision making.

Non endoscopic minimally invasive cell-collection devices like EsoCheck/EsoGuard may be considered as an acceptable alternative to upper endoscopy or as an option to screen for BE as mentioned in the 2022 American College of Gastroenterology (ACG) and American Gastroenterological Association (AGA) guidelines for screening in Barrett's Esophagus (Shaheen 2022; Muthusamy 2022).

A randomized controlled virtual patient trial is a means of obtaining clinical utility data for reimbursement (Peabody 2019).

AIM

This prospective randomized, controlled, virtual, patient study aims to assess the impact of EsoCheck/EsoGuard on health care provider's decision for upper endoscopy referral.

3. TRIAL DESIGN

This will be a prospective randomized, controlled, virtual, patient study to measure the impact of EsoCheck/EsoGuard on health care provider's decision for upper endoscopy referral.

Around 200 US physicians will be asked to participate in this study and at least 100 will be enrolled.

[figure not shown]
Physicians eligible for participation are those whose scope of practice includes preventative care and disease screening – namely screening of BE, such as primary care physicians, family medicine physicians, and general practitioners; physicians whose scope of practice include diagnosis and management of esophageal disease may also participate.

- At least 80% of the overall study population will be primary care primary care physicians, family medicine physicians, and general practitioners;
- ≤20% will be other physicians/specialists.

Eligible participants will sign the IRB approved ASBE participant Informed Consent Form (ICF).

The participants will complete two rounds of questions concerning the assessed risk for BE and decision for endoscopy referral of 6 patient cases (clinical vignettes). Per round, there will be 3 different questionnaires consisting of 6 clinical vignettes (A/B/C). Participants will be randomized to questionnaire A, B or C according to the randomization scheme. The link to the online questionnaires will be sent by email. The questionnaires should be completed within approximately ten (10) business days, and no more than twenty (20) business days after receiving the link. After the first round has been completed, an EsoCheck/EsoGuard educational information package and the second round of 6 clinical vignettes including EsoGuard results will be sent.

Flowchart

4. STUDY OBJECTIVES

This study has the following objectives:

Primary objective

To determine the impact of EsoCheck/EsoGuard on health care provider's decision for upper endoscopy referral.

Secondary objective

To determine the impact of EsoCheck/EsoGuard on health care provider's patient risk assessment for BE.

5. STUDY POPULATION

Inclusion criteria

1. Board-certified physicians whose scope of practice includes preventative care and disease screening, and/or those whose scope of practice include diagnosis and management of esophageal disease (examples include but are not limited to primary care physicians/ general practitioners, family medicine physicians, gastroenterologists, and foregut surgeons);
2. Have between 1 to 40 years of post-residency clinical experience within their field of practice;
3. Have an active panel (whether as part of a group practice, or individually) of over 1000 patients with an adult patient load of more than 50%.

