6.1 Round 1 Control

The control round consists of 8 virtual patient cases (clinical vignettes). The 3 questionnaires (A/B/C) will consist of 6 clinical vignettes with the same risk profile as in the intervention round with a different description and in a different order.

The following baseline and self-assessment questions will be asked:

- Location of practice
- Type of practice
- Number of MDs associated with the practice
- Years of practice
- Proportion of patients covered by Medicare/Commercial insurance (<50% Medicare/>50% commercial; 50/50; >50% Medicare/<50% commercial)
- Estimate of number of GERD patients seen per week (<10; 10-20; ≥20)
- Rate your knowledge of Barrett's Esophagus (BE), esophageal adenocarcinoma (EAC), and associated risk factors (1 = not knowledgeable at all; 2 = not very knowledgeable; 3 = somewhat knowledgeable; 4 = very knowledgeable; 5 = expert)
- Rate your knowledge of the options and indications for BE screening (1 = not knowledgeable at all; 2 = not very knowledgeable; 3 = somewhat knowledgeable; 4 = very knowledgeable; 5 = expert)
- Rate the frequency in which you refer your GERD patients for endoscopic BE screening, as part of your standard practice (<20%; 20-40%; 40-60%; 60-80%; ≥80%)

The following questions will be asked per clinical vignette:

1. What level of risk for BE (and/or EC) do you think this patient has?
 - Low
 - Intermediate
 - High
2. Do you refer this patient for upper endoscopy?
 - Yes, I would refer this patient for endoscopy
 - No, I would not refer this patient for endoscopy

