7.2 Power Justification

No data exist regarding the expected endoscopy referral rate for patients at risk for BE with an EsoGuard test result by primary care physicians. It is expected that if at least 100 providers participate and complete both rounds the objectives can be met. Previous randomized controlled, virtual patient trials enrolled between 81 and 202 participants (Peabody, 2019).

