7.3 Statistical formulation and statistical analysis plan of the objectives

Primary objective: To determine the impact of EsoCheck/EsoGuard on health care provider's decision for upper endoscopy referral.

The impact will be measured by assessing the change in the percentage/rate of virtual patient cases who will be referred for endoscopy in the intervention round compared to the control round.

Statistics summarizing the agreement between the EsoGuard result (positive or negative) and the health care provider's decision (referral or no referral deemed necessary) include:

- positive agreement; percentage of EsoGuard positive virtual patient cases that were referred for endoscopy
- negative agreement; percentage of EsoGuard negative virtual patient cases that were not referred for endoscopy
- positive predictive value (PPV); percentage of referred virtual patient cases that are EsoGuard positive
- negative predictive value (NPV); percentage of non-referred virtual patient cases that are EsoGuard negative
- percentage of concordance

The participant-reported impact of EsoGuard results on their clinical decision making will be measured by assessing the proportion of patient cases in round 2 for which the provider answered the question, *“Did the EsoGuard result influence your decision to refer or not refer the patient for upper endoscopy”*, with, *“Yes; the EsoGuard result had an impact on my decision”* divided by all patient cases in round 2.

The provided answers will also be reported in a table with counts and percentages.

Secondary objective: To determine the impact of EsoCheck/EsoGuard on health care provider's patient risk assessment for BE.

The impact will be measured by assessing the change in the provider's virtual patient risk assessment for BE in the intervention round compared to the control round.

The provided answers will be reported in a table with counts and percentages.

The baseline and self-assessment questions, Round 1 Control, and Round 2 Intervention, will be reported in a table with counts and percentages.

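### The referral question has no answer for a specialist who would perform the endoscopy, so a literal 'No' could be counted as a decision against endoscopy

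*Combined protocol and SAP*

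**What the plan says.** Section 5 lists "gastroenterologists, and foregut surgeons" among its examples of eligible physicians. Section 3 requires at least 80% of participants to come from primary care, family medicine or general practice, and adds that "≤20% will be other physicians/specialists".

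The outcome question in section 6.1 is "Do you refer this patient for upper endoscopy". It has two answers: "Yes, I would refer this patient for endoscopy" and "No, I would not refer this patient for endoscopy". Section 6.2 repeats both the question and the answers for round 2. Its third question, on whether EsoGuard influenced the decision, is also framed as refer or not refer.

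Section 7.3 defines the primary measure as the "change in the percentage/rate of virtual patient cases who will be referred for endoscopy in the intervention round compared to the control round". It then sets the same answer against the EsoGuard result to obtain positive and negative agreement, predictive values and concordance. There, a negative answer stands for the view that referral was not needed.

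The plan gives no option for performing the procedure oneself, no instruction on how an endoscopist should read the question, no recoding rule and no analysis by specialty. Type of practice is collected at baseline, but only to be tabulated.

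**The concern.** For a primary care physician, a negative answer has one meaning: no endoscopy is wanted. For a physician who does endoscopies it can have two: no endoscopy is wanted, or the physician would do it without referring. The scoring recognises only the first. An answer given in the second sense would lower the referral rate. It would count as disagreement when EsoGuard is positive and as agreement when EsoGuard is negative.

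At stake are the primary change in referral and, more visibly, positive agreement. Each physician sees only one EsoGuard-positive case, so that measure rests on few answers. Once the data are in, nothing recorded would tell the two meanings apart, so the size of the error could not be estimated.

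**Working it through.** **What the plan supplies.** Section 7.2 says that no data exist on the expected referral rate. It supports the minimum of 100 participants by the size of earlier trials, so there is no calculation to reproduce. The point does not depend on the sample size.

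**Inputs from the documents**
- Specialist share s: at most 0.20 (section 3).
- Round 2 cases per physician: 5 EsoGuard negative and 1 positive (section 6.2).
- Minimum participants: 100 (section 7.2).

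**Answers exposed at 100 participants with a full quota**
- Per round: 100 × 6 = 600 answers, of which 20 × 6 = 120 come from specialists.
- Round 2, EsoGuard positive: 100 answers, 20 from specialists.
- Round 2, EsoGuard negative: 500 answers, 100 from specialists.

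**Assumptions, none given in the documents**
- All the non-primary-care participants are endoscopists who would do the procedure themselves.
- A share q of them answers literally, and does so in both rounds.
- Their true decisions match those of primary care.
- True values: positive agreement 95%, negative agreement 70%, change -30 points. With these, the true round 2 rate is (0.95 + 5 × 0.30)/6 = 40.8%, so a change of -30 points implies a round 1 rate of 70.8%.

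**Formulas.** Every observed referral rate is the true rate times k = 1 - s × q. Hence:
- observed positive agreement = 0.95 × k
- observed change = -30 × k
- observed negative agreement = 1 - 0.30 × k

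**Results at s = 0.20**

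| q | k | Positive agreement | Change (points) | Negative agreement |
|---|---|---|---|---|
| 0 | 1.00 | 95% | -30.0 | 70% |
| 25% | 0.95 | 90.3% | -28.5 | 71.5% |
| 50% | 0.90 | 85.5% | -27.0 | 73.0% |
| 100% | 0.80 | 76.0% | -24.0 | 76.0% |

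If endoscopists make up only 10% of participants and all answer literally, k = 1 - 0.10 = 0.90, which is the 50% row.

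**Other summaries, from q = 0 to q = 100%**
- PPV: k cancels, so it stays at 0.95/(0.95 + 1.50) = 38.8%.
- NPV: 3.50/(3.50 + 0.05) = 98.6% becomes 3.80/(3.80 + 0.24) = 94.1%.
- Concordance: (0.95 + 3.50)/6 = 74.2% becomes (0.76 + 3.80)/6 = 76.0%.

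**Direction.** With the same reading in both rounds, k multiplies both rates. The change therefore shrinks towards zero and keeps its sign. If specialists read the question differently in the two rounds, the bias could go either way. The documents give no reason to expect such a switch.

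**The case against.** The strongest reply is that misclassification is not shown. It needs a specialist who would do the endoscopy personally and who also takes the question to exclude that. The documents do not say that these specialists scope their own patients; that is general knowledge. Section 7.3 presents the answer as a judgement of need, and an endoscopist may well read the question as whether to send the patient for endoscopy and answer yes. This stands: the error is possible, not established, and q is unknown.

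The size can also be challenged. Twenty percent is a ceiling, and the capped category covers other physicians and specialists in general, some of whom do no endoscopy. The comparison is between rounds in the same participants, so a consistent reading weakens the apparent effect and cannot create one. PPV does not move and concordance hardly does. This stands too, and limits the point to a modest one.

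Two stronger inferences fail. Section 7.2 speaks of a referral rate "with an EsoGuard test result by primary care physicians", and a reader might conclude that primary care is the target population and that pooling is therefore wrong. That sentence only reports missing prior data. Section 7.1 names both groups, and the objective concerns health care providers generally. A reader might also assume that the type-of-practice item records specialty. Section 6.1 lists no categories for it, and it may mean practice setting.

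None of this removes the ambiguity itself. The documents contain no instruction or rule that settles how such an answer is to be read.

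**Conclusion.** The point holds as a gap in the outcome item: an eligible specialist could truthfully give an answer that is scored as the opposite of the intended decision, and the data could not reveal it. The upper bound is a 20% shrinkage of all observed referral rates and of their change. It applies only if the quota is filled entirely by endoscopists who all answer literally in both rounds and whose true rates match those of primary care. At a 25% literal share the shrinkage is 5%.

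Positive agreement is the most exposed measure, losing up to 19 points in the example. Negative agreement gains up to 6 points, so the error does not run in one direction across the summaries.

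A reader might infer that the primary endpoint is already misclassified, or that the primary result could be reversed. The documents support neither: the first depends on how specialists read the question, and the second does not follow under a consistent reading. This is a cheap improvement to the instrument and the tables, and it does not undermine the design.

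**What to change.** 1. In both rounds, word the question and both answers as *refer this patient for, or perform, upper endoscopy*. The meaning of a primary care answer stays the same, and nobody is excluded.
2. Align the third question of round 2, the wording of the primary objective and the definitions in section 7.3, which repeats that third question.
3. In section 7.3, report the primary change and the agreement measures for primary care and for other physicians beside the overall result. Use the classification that the sponsor needs anyway to enforce the 80/20 split, and do not rely on the type-of-practice item. If questionnaires have already been answered, this split remains available and shows the primary care result free of the ambiguity.

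The cost is a few words in the online form, matching edits to the protocol and an extra pair of table columns. There are two downsides. The construct becomes a decision for endoscopy and is no longer strictly referral, which the sponsor should accept openly. The specialist columns will also be imprecise: at 100 participants they hold at most about 20 physicians, and so about 20 EsoGuard-positive answers.

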6. STUDY PROCEDURES

The participants will complete two rounds of questions concerning the assessed risk for BE and upper endoscopy referral of 6 patient cases (clinical vignettes). Per round, there will be 3 different questionnaires consisting of 6 clinical vignettes (A/B/C). Participants will be randomized to questionnaire A, B or C according to the randomization scheme.

The link to the online questionnaires will be sent by email. The questionnaires should be completed within approximately ten (10) business days, and no more than twenty (20) business days after receiving the link.

After the first round has been completed, an EsoCheck/EsoGuard information package and the second round of 6 clinical vignettes including EsoGuard results will be sent.

6.1 Round 1 Control

The control round consists of 8 virtual patient cases (clinical vignettes). The 3 questionnaires (A/B/C) will consist of 6 clinical vignettes with the same risk profile as in the intervention round with a different description and in a different order.

The following baseline and self-assessment questions will be asked:

- Location of practice
- Type of practice
- Number of MDs associated with the practice
- Years of practice
- Proportion of patients covered by Medicare/Commercial insurance (<50% Medicare/>50% commercial; 50/50; >50% Medicare/<50% commercial)
- Estimate of number of GERD patients seen per week (<10; 10-20; ≥20)
- Rate your knowledge of Barrett's Esophagus (BE), esophageal adenocarcinoma (EAC), and associated risk factors (1 = not knowledgeable at all; 2 = not very knowledgeable; 3 = somewhat knowledgeable; 4 = very knowledgeable; 5 = expert)
- Rate your knowledge of the options and indications for BE screening (1 = not knowledgeable at all; 2 = not very knowledgeable; 3 = somewhat knowledgeable; 4 = very knowledgeable; 5 = expert)
- Rate the frequency in which you refer your GERD patients for endoscopic BE screening, as part of your standard practice (<20%; 20-40%; 40-60%; 60-80%; ≥80%)

The following questions will be asked per clinical vignette:

1. What level of risk for BE (and/or EC) do you think this patient has?
 - Low
 - Intermediate
 - High
2. Do you refer this patient for upper endoscopy?
 - Yes, I would refer this patient for endoscopy
 - No, I would not refer this patient for endoscopy

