6.2 Round 2 Intervention

The intervention round consists of 8 EsoGuard patient cases (clinical vignettes) (3 positive and 5 negative for EsoGuard). The 3 questionnaires (A/B/C) will have the same 5 negative EsoGuard cases, and 1 (different) positive EsoGuard case per questionnaire.

The following questions will be asked per clinical vignette:

1. What level of risk for BE (and/or EC) do you think this patient has?
 - Low
 - Intermediate
 - High
2. Do you refer this patient for upper endoscopy?
 - Yes, I would refer this patient for endoscopy
 - No, I would not refer this patient for endoscopy
3. Did the EsoGuard result influence your decision to refer or not refer the patient for upper endoscopy?
 - Yes; the EsoGuard result had an impact on my decision
 - No; the EsoGuard result had no impact on my decision

The following self-assessment questions will be asked of each participant at the end of round two (scale 1 very low to 5 high):

- Rate your understanding of EsoCheck/EsoGuard and its indications?
- How likely are you to use EsoCheck/EsoGuard for BE screening in your own practice?
- How likely are you to refer this technology to others or use in their practices?

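### Each set of vignette descriptions is tied to one round, so any residual difference between the sets cannot be separated from the EsoGuard effect in the between-round changes

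*Combined protocol and SAP*

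**What the plan says.** - **Texts.** Section 6.1 describes the Round 1 questionnaires as "6 clinical vignettes with the same risk profile as in the intervention round with a different description and in a different order". Each round has a pool of 8 cases, of which each physician sees 6 (Sections 6.1 and 6.2).
- **Round 2 content.** There are three EsoGuard-positive and five EsoGuard-negative cases. Under Section 6.2, questionnaires A, B and C "will have the same 5 negative EsoGuard cases, and 1 (different) positive EsoGuard case per questionnaire".
- **Randomization.** Section 6: "Participants will be randomized to questionnaire A, B or C according to the randomization scheme". Neither the order of the rounds nor the assignment of descriptions to rounds is said to be randomized. The scheme itself is not reproduced.
- **Sequence.** Section 6: "After the first round has been completed, an EsoCheck/EsoGuard information package and the second round of 6 clinical vignettes including EsoGuard results will be sent". Control comes first for everyone.
- **Primary measure.** Section 7.3 takes the "change in the percentage/rate of virtual patient cases who will be referred for endoscopy in the intervention round compared to the control round". The secondary measure is the corresponding change in risk rating. Section 7.3 states no model, vignette term or hypothesis test.

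**The concern.** The control vignette is not the intervention vignette with the EsoGuard result removed. It is another text, which the authors regard as carrying the same risk. Using fresh text is a sensible guard against recall. The difficulty is that each text belongs permanently to one round, so description set and EsoGuard exposure vary together.

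If the Round 2 texts happen to read as somewhat milder or more worrying than their Round 1 counterparts, physicians may refer less or more for that reason alone, and the between-round difference would count this as impact of the test. The trial's own data cannot reveal it. The study is meant to supply clinical utility evidence for reimbursement, so the size of the referral change matters as well as its sign.

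**Working it through.** **Is there a plan figure to reproduce?** No. Section 7.2 says only that "It is expected that if at least 100 providers participate and complete both rounds the objectives can be met" and gives no referral rate, effect size, significance level or power. The point is structural. The rates and wording effects used below are assumptions.

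**Step 1: does the text leave room for a swap?** Eight risk profiles with two descriptions each make 8 × 2 = 16 texts. If physicians were split over which set they received in Round 2, Round 2 would contain 16 texts, not the 8 that Section 6.2 states. The five negative cases would also no longer be the same across questionnaires. A swap does not fit Sections 6.1 and 6.2 as written. The five common negatives make up 5/6 = 83% of each physician's Round 2 decisions; the single positive case (1/6 = 17%) varies by questionnaire.

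**Step 2: what does the planned difference estimate?** Let X be the Round 1 descriptions and Y the Round 2 descriptions. Let r0(·) be the mean referral rate under control-round conditions and r1(·) the rate under intervention-round conditions. Define:

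- d0 = r0(Y) − r0(X), the wording difference without a result
- d1 = r1(Y) − r1(X), the wording difference with a result
- E(X) = r1(X) − r0(X) and E(Y) = r1(Y) − r0(Y), the effects on each set

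The planned change is r1(Y) − r0(X). This equals E(X) + d1, and also E(Y) + d0. Averaging the two expressions gives [E(X) + E(Y)]/2 + (d0 + d1)/2.

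**Step 3: how much passes through?** Bias against the effect averaged over both sets is (d0 + d1)/2:

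| Assumed d0 (points) | Wording acts equally with and without a result (d1 = d0) | Round 2 decisions follow the result only (d1 = 0) |
|---|---|---|
| 2 | 2 | 1 |
| 5 | 5 | 2.5 |
| 10 | 10 | 5 |

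If d1 = 0 and the target is the effect on the Round 1 texts, the bias is zero. If the target is the effect on the Round 2 texts, it is d0 in full.

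**Step 4: does sample size help?** Treat decisions as independent, which is a simplification because they are clustered and paired within physician. The standard error of the change is then √[2p(1 − p)/n].

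- 100 physicians × 6 = 600 decisions per round: √(2 × 0.3 × 0.7/600) = 2.6 points at p = 30% (the same at 70%), and √(2 × 0.5 × 0.5/600) = 2.9 points at p = 50%.
- If all of the roughly 200 invited physicians took part, 1,200 decisions per round: √(0.5/1200) = 2.0 points at p = 50%.

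Now suppose each description shifts referral at random and additively with SD s, independently of the others, and Round 1 has the same layout as Round 2 (five common cases, plus one of three in equal thirds). The SD of the bias is s × √{2 × [5 × (1/6)² + 3 × (1/18)²]} = 0.544s. For s = 5, 10 or 15 points this is 2.7, 5.4 or 8.2 points. No term contains the number of physicians, so at s = 10 the SD of the bias is 5.4 points with 100 or 200 participants.

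**Step 5: what would a swap do?** One sequence estimates r1(Y) − r0(X) and the other r1(X) − r0(Y). Their equal average is [r1(X) + r1(Y)]/2 − [r0(X) + r0(Y)]/2 = [E(X) + E(Y)]/2. Both d0 and d1 drop out, so this does not require wording to act equally with and without a result. It does assume that the carry-over into Round 2 does not depend on which set was read first.

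**The case against.** The best defence is that the vignettes are matched on risk profile. On a natural reading, the clinical details that drive referral are what is held constant, leaving only phrasing. The vignettes are not in the documents, so no actual mismatch can be shown. This stands as a limit on the likely size. It does not remove the point: the protocol does not define the profile, describes no equivalence check, and has no design feature that would reveal a mismatch.

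Several stronger readings are tempting, and the documents do not support them:

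- **That the design favours the product.** The direction of any wording difference is unknown.
- **That the full difference always passes through.** This holds if wording acts equally with and without a result, or if the Round 2 texts define the target. It is less if Round 2 decisions mainly follow the result.
- **That every physician reads identical Round 2 text.** This is true of the five negatives but not of the one positive case.
- **That the plan has an inflated false-positive rate.** Section 7.3 specifies no test, so there is no error rate to inflate.
- **That the protocol rules out a swap explicitly.** The randomization scheme is not reproduced. The conclusion rests on Sections 6.1 and 6.2 leaving no room for a swap and on the absence of any mention of one.

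It is also fair to say that a swap leaves the fixed round order and the information package in place, and that these may matter more than wording. That limits what the fix achieves but is no reason to leave a removable source of bias.

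**Conclusion.** The point holds as a design weakness that should be corrected. As written, description set and EsoGuard exposure are aliased in the primary referral change and the secondary risk-rating change. Matching on risk profile limits the resulting bias, but equivalence is assumed and cannot be tested from the trial data.

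The documents allow no estimate of the actual bias. The figures in the table show only how an assumed difference would carry over, and the sign could go either way. A large EsoGuard effect might well exceed a small wording bias, but its size would still be misestimated.

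The remaining Section 7.3 measures for the primary objective (positive and negative agreement, PPV, NPV, concordance and the per-case question on influence) involve no comparison with Round 1 and are not affected by this route.

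A reader might infer that counterbalancing the descriptions would isolate the effect of EsoGuard. It would not: every physician still does the control round first and receives the information package before Round 2. The between-round change should be attributed to the combined intervention.

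**What to change.** 1. Within each of A, B and C, randomize physicians 1:1 to set X in Round 1 and set Y in Round 2, or the reverse. Add the EsoGuard result to whichever set is used in Round 2.
2. Amend Sections 6.1 and 6.2 to match, distinguishing the 8 risk profiles from the two descriptions of each and stating that the five negatives are common as profiles. If the existing scheme already includes a swap, say so there.
3. In Section 7.3, compute the between-round change in each sequence and average the two with equal weight, for both referral and risk rating. Simple pooling would leave a remainder if completion were uneven: with an assumed 55/45 split and an additive difference d, 0.55d − 0.45d = 0.10d.
4. Word the conclusion as the effect of the information package and the EsoGuard result together, in a fixed round order.

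The cost is six allocation cells instead of three, plus extra survey links. Both sets of descriptions have to exist already, and recall protection is unchanged because no physician reads the same text twice. A pilot equivalence check would be a useful addition but not a substitute, since it could not guarantee that the sets are equivalent both with and without a result.
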